## 7.3 Center Pooling

No poolability analyses are planned.

# 7.4 Handling of Missing, Unused, and Spurious Data and Dropouts

Every effort will be undertaken to minimize missing data. In time-to-event outcomes, drop-outs will be censored at the time of discontinuation, consistent with the Kaplan-Meier approach.

Unless otherwise specified in each objective, no statistical techniques will be used to impute missing data for continuous or categorical outcomes. If a subject's data are missing for any reason, that subject will not be included in that portion of the analysis. Erroneous (i.e., incorrect including withdrawal and drop out) and abnormal data will be cleaned prior to performing the database snapshot for the statistical analyses. The number of subjects included in each analysis will be reported so that the reader can assess the potential impact of missing data. Sensitivity analysis will be conducted for primary endpoints.

In the case of partial dates, if only the month and year are known, the event or assessment will be analyzed as if it occurred on the 15th of that month. If only the year is known, the event or assessment will be analyzed as if it occurred on June 30th of that year. These resolutions of partial dates are subject to all the reasonable restrictions, for example, pre-procedure events and assessments must occur between the enrollment date and the procedure date, post-procedure events and assessments must occur no earlier than the procedure date, and AE awareness date must be on or later than AE onset date.

Revision 3.0

Page 15 of 23

## 7.5 Use of Echocardiographic Data

### 7.5.1 Echo Core Lab

An independent Echo Core Lab will evaluate all echocardiograms through the 30-day follow up assessment. Echocardiographic-related primary and secondary endpoints will be based on the core lab assessments. As the study has transitioned to post-market, further echocardiographic-related data and results will be site-reported.

## 7.5.2 Echocardiographic Data After Reinterventions

Unless otherwise specified, echocardiographic data collected after reinterventions will be excluded from all analyses, as the reported data is not associated with the implanted index valve's performance.

At the time of the primary endpoint analysis, no reinterventions occurred in any subjects prior to the 30 day visit and the primary endpoint analysis included all available echos.

## 7.6 Adjustments for Multiple Comparisons

There are no planned multiple comparisons expected and thus no multiplicity adjustments are planned for this study.

## 7.7 Demographic and Other Baseline Characteristics

Descriptive statistics, as defined in 7.2.1, will be used to report demographic and clinical characteristics at baseline. Major baseline demographic and clinical variables will be summarized for the attempted implant analysis set as defined in 7.1.3.

## 7.8 Treatment Characteristics

[figure not shown]
Descriptive statistics, as defined in 7.2.1, will be used to report procedure characteristics for the attempted implant analysis set as defined in 7.1.3. Information to be summarized includes, but is not limited to, variables such as valve sizes, anesthesia type, and access route.

## 7.9 Interim Analyses

Interim analysis and corresponding early termination criteria are not planned for this trial. Hence, this section is not applicable. All statistical analysis will be performed after completing data collection, data review and data cleaning is confirmed.

Revision 3.0

Page 16 of 23

## 7.10 Evaluation of Objectives

#### **Primary Safety Objective** 7.10.1

All-cause mortality at 30 days.

#### Hypothesis/Decision criteria:

No specific hypotheses or pass/fail criteria have been set. The analysis will be descriptive, and no statistical hypothesis test will be performed.

#### Endpoint Definition/Parameters to Be Estimated:

The endpoint is the KM event rate of all-cause mortality at 30 days post procedure.

#### Data Collection and Analysis Method:

Data will be collected on event case report form (CRF). Death will be adjudicated by the CEC. CEC adjudicated all-cause mortality will be used in the analysis.

#### Analysis Dataset:

This objective will be analyzed for all subjects in the attempted implant set.

#### **Sensitivity Analysis:**

Sensitivity analysis will be performed using the following criteria. Proportions and 95% confidence intervals under each scenario will be reported:

- Complete analysis: excludes all subjects that dropped out or withdrew before 30 days
- Worst-case analysis: assumes all subjects that dropped out or withdrew before 30 days are dead
- Best-case analysis: assumes all subjects that dropped out or withdrew before 30 days are alive
- Tipping point analysis: if the number of missing subjects is n (n>1), a stepwise analysis between the best-case and worst-case scenarios will be conducted by the following steps:
  - Step 1: assumes one subject is dead, n-1 subjects alive, and calculate the proportion.
  - Step 2: assumes two subjects are dead, n-2 subjects alive, and calculate the proportion.

The calculation will be iterative until the last step: assumes n-1 subjects are dead, one subject alive, and calculate the proportion.

#### 7.10.2 **Primary Efficacy Objective**

The percentage of evaluable echocardiograms with moderate or severe aortic regurgitation at 30 days by transthoracic echocardiography (TTE).

#### Hypothesis/Decision criteria:

No specific hypotheses or pass/fail criteria have been set. The analysis will be descriptive, and no statistical hypothesis test will be performed.

## Endpoint Definition/Parameters to Be Estimated:

The endpoint is the percentage of evaluable echocardiograms with moderate or severe aortic regurgitation at 30 days by transthoracic echocardiography (TTE).

Revision 3.0

Page 17 of 23

#### Data Collection and Analysis Method:

Data will be collected in the ECHO CORE LAB CRF at 30-days post procedure. Frequency and percent of moderate or severe aortic regurgitation will be analyzed. To calculate the percent of moderate or severe aortic regurgitation, the numerator will be the number of patients with total Aortic Prosthetic Regurgitation on the ECHO CORE LAB CRF equals to moderate, moderate to severe, and severe at 30-day post procedure, and the denominator will be the number of patients whose 30-day total aortic regurgitation are not missing.

#### Analysis Dataset:

This objective will be analyzed for all subjects in the implanted set.

#### Sensitivity Analysis:

For primary efficacy endpoint, the primary outcome will be calculated by excluding subjects whose 30 days echo data were not evaluable. A sensitivity analysis will be performed using the following criteria. Proportion and 95% confidence interval under each scenario will be reported:

- Worst-case analysis: assumes all unable-to-be-assessed cases are failures
- Best-case analysis: assumes all unable-to-be-assessed cases are successes
- Tipping point analysis: if the number of missing subjects is n (n>1), a stepwise analysis between the best-case and worst-case scenarios will be conducted by the following steps:
  - Step 1: assumes one subject is dead, n-1 subjects alive, and calculate the proportion.
  - Step 2: assumes two subjects are dead, n-2 subjects alive, and calculate the proportion.

The calculation will be iterative until the last step: assumes n-1 subjects are dead, one subject alive, and calculate the proportion.

#### 7.10.3 **Secondary Safety Objectives**

### 1. The VARC II Combined Safety Endpoint at 30 days

#### Hypothesis/Decision criteria:

No specific hypotheses or pass/fail criteria have been set. The analysis will be descriptive, and no statistical hypothesis test will be performed.

[figure not shown]
#### Endpoint Definition/Parameters to Be Estimated:

The VARC II Combined Safety Endpoint at 30 days, which includes the following components:

- All-cause mortality
- All stroke (disabling and non-disabling)
- Life-threatening bleeding
- Acute kidney injury: stage 2 or 3 (including renal replacement therapy)
- o Coronary artery obstruction requiring intervention
- Major vascular complication
- Valve-related dysfunction requiring repeat procedure (BAV, TAVI, or SAVR)

Revision 3.0

Page 18 of 23

#### Data Collection and Analysis Method:

Data will be collected on event case report form. The safety endpoints will be adjudicated by the CEC. CEC adjudicated results will be used in the analysis. The corresponding Clinical Events Committee (CEC) codes are provided in the Clinical Events Committee (CEC Charter).

A Kaplan-Meier analysis will be performed for the VARC II Composite Safety Endpoint at 30 days post procedure.

#### **Analysis Dataset:**

This objective will be analyzed for all subjects in the attempted implant set.

#### 2. Event rates of the individual components of the VARC II composite safety endpoint at 30 days

#### Hypothesis/Decision criteria:

No specific hypotheses or pass/fail criteria have been set. The analysis will be descriptive, and no statistical hypothesis test will be performed.

#### Endpoint Definition/Parameters to Be Estimated:

Individual components of the VARC II composite safety endpoint at 30 days includes the following components:

- All-cause mortality
- All stroke (disabling and non-disabling)
- Life-threatening bleeding
- Acute kidney injury: stage 2 or 3 (including renal replacement therapy)
- Coronary artery obstruction requiring intervention
- Major vascular complication
- Valve-related dysfunction requiring repeat procedure (BAV, TAVI, or SAVR)

#### Data Collection and Analysis Method:

Data will be collected on event case report form. The safety endpoints will be adjudicated by the CEC. CEC adjudicated results will be used in the analysis. The corresponding Clinical Events Committee (CEC) codes are provided in the Clinical Events Committee (CEC Charter).

A Kaplan-Meier (KM) analysis will be performed for each individual component of the VARC II Composite Safety Endpoint at 30 days post procedure.

#### Analysis Dataset:

This objective will be analyzed for all subjects in the attempted implant set.

[figure not shown]
#### 3. New permanent pacemaker at 30 days

#### Hypothesis/Decision criteria:

No specific hypotheses or pass/fail criteria have been set. The analysis will be descriptive, and no statistical hypothesis test will be performed.

Revision 3.0

Page 19 of 23

## Endpoint Definition/Parameters to Be Estimated:

The endpoint is the KM event rate of new permanent pacemaker at 30 days post procedure.

#### Data Collection and Analysis Method:

Data will be collected on event case report form. Site reported New permanent pacemaker will be used in the analysis. Subjects with a pacemaker or ICD at baseline will be excluded.

#### Analysis Dataset:

This objective will be analyzed for all subjects in the attempted implant set.

#### 7.10.4 **Secondary Efficacy Objectives**

#### 1. Device success at 24 hours to seven days

#### Hypothesis/Decision criteria:

No specific hypotheses or pass/fail criteria have been set. The analysis will be descriptive, and no statistical hypothesis test will be performed.

## Endpoint Definition/Parameters to Be Estimated:

Device success at 24 hours to seven days, defined as:

- Absence of procedural mortality, AND
- Correct positioning of a single prosthetic heart valve into the proper anatomical location, AND
- o Intended performance of the prosthetic heart valve, defined as the absence of patient prosthesis-mismatch and mean aortic valve gradient less than 20 mmHg (or peak velocity <3m/sec), AND absence of moderate or severe prosthetic valve regurgitation

[figure not shown]
#### Data Collection and Analysis Method:

The components of device success will be determined as follows:

- No death event occurs within 30 days post-procedure, or on or before the discharge date (if the discharge date is longer than 30 days post-procedure);
- In the procedure CRF, the answer to "Correct positioning of the prosthetic heart valve into proper anatomical location" and "only 1 TAV implanted" should be both "YES";
- The criteria for ECHO will be based on the ECHO Core Lab Data for the time interval of 24 hours to 7 days:
  - Mean aortic gradient < 20 mmHg or peak velocity < 3 m/sec;
  - Absence of moderate or severe prosthetic valve regurgitation. Total Aortic Prosthetic Regurgitation on the ECHO CORE LAB form is less than moderate.
  - Absence of patient-prosthesis-mismatch:
    - For subjects with BMI < 30 kg/m2, index effective orifice area (EOAi) > 0.85 cm2 /m2

Revision 3.0

Page 20 of 23

For subjects with BMI ≥ 30 kg/m2, index effective orifice area (EOAi) > 0.70 cm2 /m2

BMI = weight(kg)/(height (m)) 2, where weight and height are recorded on the ECHO CORE LAB form.

All the above components must be satisfied to count as a device success. If any of the above components fails, the endpoint will be counted as a failure.

For the overall device success rate, the numerator will be the number of subjects whose procedures result in device success as described above, and the denominator will be the number of subjects whose device success results are not missing. Note that this analysis excludes those subjects with a missing response to any of the above three components (e.g., the field "Post-implant Severity of Total Aortic Regurgitation" = "Unable to Assess" or "Not Recorded", missing mean aortic gradient, or missing peak velocity, etc.) and without a "NO" response to any of the components. The binary rate of device success and the exact two-sided 95% confidence interval will be estimated.

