- Left ventricular ejection fraction by visual estimate

[figure not shown]
Qualitative grading of valvular regurgitation will be performed using the criteria described in Sections 4.4 through 4.6. For reporting the degree of prosthetic regurgitation, the grading classes may be collapsed according to the 3-class grading scheme recommended by the American Society or Echocardiography (ASE)-European Association of Cardiovascular Imaging Guidelines.³⁹

In addition, the following variables will be derived by the central database from the appropriate measurements reported by the Echo Core Lab:

Peak Pressure Gradient (Peak Δ P) Across the Aortic Valve in mmHg Peak Δ P = 4 x (V₂²)

Where: V2 is the peak velocity across the prosthesis in m/sec

Aortic Valve Area (AVA) in cm²

Medtronic

AVA = LVOT diameter in cm² x 0.785 x (VTI_{V1}/VTI_{V2})

Where: VTI_{V1} is the velocity time integral of the left ventricular outflow tract in cm, and VTI_{V2} is the velocity time integral of the native aortic valve in cm

 Aortic Valve Area Index (AVAI) in cm²/m² AVAI = AVA/BSA

Where: AVA is the native aortic valve area in cm², and BSA is the body surface area in m²viii

Effective Orifice Area (EOA) in cm²
 EOA = LVOT diameter² x 0.785 x (VTI_{V1}/VTI_{V2})

Where: VTI_{V1} is the velocity time integral of the left ventricular outflow tract in cm, and VTI_{V2} is the velocity time integral of the aortic prosthesis in cm

 Effective Orifice Area Index (EOAI) in cm²/m² EOAI = EOA/BSA

Where: EOA is the effective orifice area in cm², and BSA is the body surface area in m²

• Doppler Velocity Index (DVI)

 $DVI = VTI_{V1}/VTI_{V2}$

Where: VTI_{V1} is the velocity time integral of the left ventricular outflow tract in cm, and VTI_{V2} is the time velocity integral of the prosthetic aortic valve in cm

Estimated Right Ventricular Systolic Pressure (RVSP) in mmHg

 $RVSP = (4 \times MVTR jet^2) + 10$

Where: MV TR jet is the max velocity of the tricuspid regurgitant jet, and 10 = the assumed mean right atrial pressure in mmHg

Body Surface Area (BSA) in m²
 BSA = 0.007184 x (height in cm^{0.725} x weight in kg^{0.425})

_

viii BSA derived from height and weight reported on the site eCRF

MDT18065EVR009 Version 5.0 06-Oct-2023

Page 93 of 121

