## 6. Determination of Sample Size

As this is not a powered hypothesis-driven study, the sample size of 50 attempted subjects was not determined by statistical methods. Rather, it was based on adherence to the NMPA TAVI Clinical Trial Guideline and was confirmed during the NMPA consultation meetings and protocol synopsis submitted with no further objections/feedback (October 2018 through March 2019).

The total sample size of the primary study population is 50 attempted implants, exclusive of the roll-in population. There is no minimum number of subjects required for each clinical institution. No site will implant more than 20 subjects, excluding the roll-in subjects, without prior authorization from Medtronic.

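### Device success (SAP 7.10.4): the exclusion rule conflicts with its own either/or gradient-velocity criterion, and removing unresolved subjects gives a rate that can be biased in either direction

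*SAP*

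**What the plan says.** SAP 7.10.4 builds device success from three components: no procedural death, correct placement of a single valve, and a set of core-lab echo criteria at 24 hours to 7 days. All must be met, and failure of any one is a failure overall. The echo set needs acceptable gradient or velocity, less than moderate total regurgitation, and no patient-prosthesis mismatch.

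- **Gradient/velocity criterion:** "Mean aortic gradient < 20 mmHg or peak velocity < 3 m/sec".
- **Missing data:** "Note that this analysis excludes those subjects with a missing response to any of the above three components". The sentence adds a second condition, that no component carries a NO. Its examples of a missing response include "missing mean aortic gradient, or missing peak velocity".
- **Interval:** an exact two-sided 95% interval on the subjects whose result is not missing, although the named analysis set is all attempted implants.
- **BMI for the mismatch cut:** computed from weight and height, "where weight and height are recorded on the ECHO CORE LAB form".
- **Sensitivity analysis:** SAP 7.4 plans it for the primary endpoints. SAP 7.10.2, for instance, has "Worst-case analysis: assumes all unable-to-be-assessed cases are failures" and the matching best case. Device success has none.

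**The concern.** There are three difficulties.

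1. The criterion and the missing-data examples do not agree. A subject with a gradient of 12 mmHg and no recorded peak velocity meets the either/or criterion, yet has one of the listed reasons for exclusion. Two programmers could reach different denominators from the same data.
2. A subject with an incomplete echo and a recorded failure elsewhere is counted as a failure. A subject with an incomplete echo and nothing failed so far is removed. The remaining set is therefore selected on outcome, and its rate need not equal the rate over all attempted implants.
3. The variables that Protocol Appendix II, Section 5.0 requires the core lab to report include neither height nor weight. Protocol 9.2.5 and Appendix II, Section 3.0 have the sites record them, and a footnote to Section 5.0 reads "BSA derived from height and weight reported on the site eCRF". BMI selects which indexed orifice-area threshold applies, so its source has to be settled.

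At stake are the accuracy of a reported secondary rate and whether its interval conveys how much depends on unmeasured subjects.

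**Working it through.** **Inputs from the documents.** "The total sample size of the primary study population is 50 attempted implants, exclusive of the roll-in population" (SAP 6). This agrees with 58 attempted less 2 roll-ins at each of 4 sites: 58 − 8 = 50. The plan states no expected device-success rate and no missing-echo rate for the 24-hour-to-7-day visit, so there is no figure to reproduce. Every rate and count below is an assumption.

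**Whole echo missing at random.** Let s be the true success rate, m the share with no echo, and f the probability of a known failure on a non-echo component. The rule reports R = (1−m)s / [(1−m) + m·f].

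| s | f | m = 10% | m = 20% | m = 30% |
|---|---|---|---|---|
| 85% | 8% | 0.765/0.908 = 84.3% | 0.680/0.816 = 83.3% | 0.595/0.724 = 82.2% |
| 80% | 10% | 0.720/0.910 = 79.1% | 0.640/0.820 = 78.0% | 0.560/0.730 = 76.7% |

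The shift is downward, by 0.7 to 3.3 points.

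**Single items missing at random.** Now R = P(all items observed and passed) / [that + P(at least one observed NO)]. Take failure rates of 5% (non-echo), 3% (gradient), 2% (regurgitation) and 15% (mismatch), with 5% missing on each echo item. True success is 0.95 × 0.97 × 0.98 × 0.85 = 76.8%. All observed and passed is 0.7676 × 0.95³ = 0.6581. At least one observed NO is 1 − 0.95 × 0.9715 × 0.981 × 0.8575 = 0.2236. So R = 0.6581/0.8817 = 74.6%, which is 2.1 points low. Across the settings tried, the shift ran from −0.6 to −6.2 points. The largest had 10%, 10% and 20% missing on the three items.

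**Echo failures missing more often.** Let e be the echo failure rate, and m0 and m1 the missing rates among echo passes and echo failures. With S = (1−f)(1−e), R = S(1−m0) / [S(1−m0) + f + (1−f)e(1−m1)]. Take f = 5%, e = 20%, m0 = 10%. Then S = 76.0% and the numerator is 0.684.

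- m1 = 10%: 0.684/0.905 = 75.6% (−0.4)
- m1 = 15%: 0.684/0.8955 = 76.4% (+0.4)
- m1 = 30%: 0.684/0.867 = 78.9% (+2.9)
- m1 = 40%: 0.684/0.848 = 80.7% (+4.7)

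The bias is zero when f + (1−f)e(1−m1) = (1−S)(1−m0), that is 0.05 + 0.19(1−m1) = 0.216, giving m1 = 12.6%. Missingness only 1.26 times as high among echo failures cancels the downward bias here. Across the settings tried, the ratio was 1.10 to 2.11.

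**Bounds at n = 50.** Suppose 36 complete successes, 7 complete failures, 2 incomplete subjects with a NO, and 5 incomplete subjects without one (intervals are exact 95%).

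- Rule as written: 36/45 = 80.0% (65.4-90.4)
- Unresolved as failures: 36/50 = 72.0% (57.5-83.8)
- Unresolved as successes: 41/50 = 82.0% (68.6-91.4)

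**Either/or conflict alone.** If 40 of 50 truly succeed, dropping 1, 3 or 5 successes because one of the two measures is absent gives 39/49 = 79.6%, 37/47 = 78.7% or 35/45 = 77.8%, against 80.0%.

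**The case against.** **Counting a known NO as a failure is correct.** In a composite where every component must pass, a subject with a death or a second valve has failed whatever the echo shows. This stands. The difficulty is removing the unresolved subjects without bounds.

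**The missing-data examples are only illustrative.** One can argue that a gradient below 20 mmHg decides the component, so its response is not missing. That reading is possible, but the SAP does not state it. The situation may also be uncommon: Protocol Appendix II, Section 4.3 takes peak velocity, mean gradient and valve VTI from the same Doppler curve, and orifice area needs that VTI. This limits the likely size but does not remove the conflict.

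**The core-lab form is not in the documents.** It may carry height and weight. What can be said is that the protocol's variable list does not show them and its footnote points to the site form. No effect on the rate has been shown.

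**The endpoint is secondary and descriptive.** SAP 7.10.4 states: "The analysis will be descriptive, and no statistical hypothesis test will be performed". SAP 7.4 also requires the number analysed to be reported so that readers can judge missing data. That helps, but the count alone does not separate retained known failures from removed unresolved subjects. Any complete-case interval has this limit, so bounds are a proportionate addition and their absence breaks no rule of the plan.

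**A tempting stronger reading** is that the rule systematically understates success. The documents do not support it. The direction depends on why echoes are missing, on which they say nothing for this visit. Protocol 10.4 expects little missing data, but only for the 30-day primary endpoints.

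**Conclusion.** The point holds as an internal conflict plus an unbounded complete-case estimate. Read literally, SAP 7.10.4 can exclude a subject who meets its own gradient/velocity criterion. Removing unresolved subjects can bias the rate downward under random missingness, and upward once echo failures are missing modestly more often.

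The size rests on assumed missing rates. It is about 1-3 points with 10-30% of whole echoes missing at random, and more if individual items are often missing. This is small beside sampling error: the exact interval at 40/50 is 66.3% to 90.0%. The 10-point spread between bounds in the illustration (72.0% to 82.0%) is what the planned interval does not convey. If few or no subjects are indeterminate, the numerical effect is negligible, though the wording still needs correcting.

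**What to change.** - Treat the gradient/velocity component as evaluable whenever an available measure decides it. If the one measure present does not meet its limit and the other is absent, the component is undecided and counts as missing.
- Keep known failures as failures.
- Take height and weight for BMI from the site eCRF, or reconcile SAP 7.10.4 with Protocol Appendix II, Section 5.0.
- Report the number indeterminate, with best-case and worst-case rates and exact intervals over all 50 attempted implants, following SAP 7.10.2.

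Protocol 10.1.2 says the secondary endpoint analysis was completed under CIP Version 4.0. The revised figures would therefore follow a rule changed after the data were analysed, and should be labelled supplementary beside the reported rate. The cost is a few lines of SAP text and one additional table. The downside is an extra pair of figures and a wider reported range.
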